12.7.2.2. Progression Free Survival per Investigator

The secondary endpoint of PFS is defined as the time from randomization to the first occurrence of documented disease progression as determined by the Investigator and the institutional radiologist(s) per RECIST v1.1 or death from any cause, whichever occurs first.

The same censoring rules as the primary endpoint of PFS will be applied to PFS per Investigator.

A log-rank test stratified by the randomization stratification factor will be used to compare the PFS between the AG-120 vs. placebo arm. A Cox regression model stratified by the randomization stratification factor will be used to estimate the HR of PFS comparing the AG-120 arm with the placebo arm, along with the 95% CI.

Kaplan-Meier estimates of PFS, including estimates of the median and other quantiles, as well as individual time points (eg, 3-month, 6-month, and 12-month rates), will be presented for each treatment arm.

12.7.2.3. Objective Response Rate

For the secondary efficacy endpoints of ORR, DOR, and TTR, analyses will be performed using Investigator- and IRC-assessed response.

Objective response rate is defined as the rate of confirmed CR and PR per RECIST v1.1.

A summary of best objective response by arm will be produced. A Cochran-Mantel-Haenszel (CMH) test will be used to compare ORR between the 2 treatment arms. A logistic regression model may be used to estimate the treatment effect in terms of an odds ratio. The odds ratio and its associated 95% CIs will be presented.

12.7.2.4. Duration of Response

Among responders who achieve confirmed CR or PR, DOR will be calculated from the date of the first occurrence of response to the date of first documented disease progression or death. Kaplan-Meier methods will be used to estimate DOR; subjects without progression or death will be censored at the last response assessment date. Detailed censoring rules will be included in the SAP.

Kaplan-Meier estimates of DOR will be presented by arm, including estimates of the median and other quantiles, as well as individual time points (eg, 3-month, 6-month, and 12-month rates).

12.7.2.5. Time to Response

Among responders, time to response will be assessed from the date of randomization to the date of first occurrence of confirmed response per RECIST v1.1. TTR will be tabulated by arm.

12.8. Analyses of Health-Related Quality of Life and Health Economic Outcomes

12.8.1. Health-Related Quality of Life Analyses

The EORTC-QLQ-C30, EORTC-BIL21, PGI-C, and PGI-S questionnaires will be used to collect data on the subject's functioning, disease-related symptoms, HRQOL, and health status. If a subject is not able to speak any language that is covered by the EORTC-QLQ-C30, EORTC-QLQ-BIL21, PGI-C, or PGI-S, the data from those instruments will be missing throughout the duration of that subject's involvement in the study. The number and percentage of subjects with the entire questionnaire missing will be summarized by treatment. Details including the missing data handling will be specified in the SAP.

Descriptive statistics (eg, means and medians) will be used to summarize the individual items and sub-scale scores of HRQOL data as well as PGI-C and PGI-S scores at each scheduled assessment time point by treatment. Additionally, change from baseline in the domain scores at the time of each assessment will be summarized by treatment. A repeated measurements analysis model may be used to compare the two treatment groups with respect to changes in the HRQOL domain scores as well as the PGI-C and PGI-S scores longitudinally over time. In addition, anchor-based method will be used to analyze the key domains with the specific anchor questions (PGI-C and PGI-S).

Detailed analysis plan will be specified in the SAP.

12.8.2. Health Economic Outcomes Analyses

EQ-5D-5L scores will be summarized by descriptive statistics for treatment arms.

12.9. Exposure and Safety Analyses

Safety will be evaluated by the incidence of AEs, causality, severity, seriousness, and type of AEs, and by the subject's vital signs, ECOG performance scores, clinical laboratory test results, ECG, and LVEF data (as clinically indicated).

A summary of study drug exposure, including total dose, duration of treatment, dose intensity, and the proportion of subjects with dose modifications will be summarized by treatment arm. Reasons for dose modifications will be listed by subject and summarized.

Concomitant medications will be listed by subject and will be summarized by treatment arm.

All safety data will be listed by subject and summarized by treatment arm.

12.9.1. Adverse Events

Summary tables and listings for adverse events will include treatment-emergent adverse events (AEs), where AE is defined as any AE that occurred between the first dose of any study drug and 28 days following the last dose of any study drug. The incidence of AEs (new or worsening from

baseline) will be summarized according to the Medical Dictionary for Regulatory Activities (MedDRA) by system organ class and/or preferred term, severity (based on NCI CTCAE v4.03 grading as assessed by the Investigator), seriousness, and relation to study treatment. The following summaries will be produced:

- All AEs
- AEs leading to dose modifications
- Treatment-related AEs
- Grade 3 or higher AEs
- Grade 3 or higher treatment-related AEs
- The most commonly reported AEs (ie, those events reported by $\geq 10\%$ of all subjects)
- SAEs
- Discontinuations due to AEs

By-subject listings will be provided for on-treatment deaths (on-treatment is defined as the period starting from the first dose to 28 days after the last dose), AEs, SAEs, and AEs leading to discontinuation of treatment.

12.9.2. Laboratory Abnormalities

For laboratory tests included in the NCI CTCAE version 4.03, laboratory data will be graded accordingly; a Grade 0 will be assigned for all non-missing values not graded as 1 or higher. For laboratory tests where grades are not defined by NCI CTCAE, results will be graded by the low/normal/high classifications based on laboratory normal ranges.

The following summaries will be generated separately for hematology, serum chemistry and coagulation studies, and urinalysis laboratory tests:

- Descriptive statistics for the actual values and/or change from baseline of clinical laboratory parameters over time.
- Shift tables using NCI CTCAE grades to compare baseline to the worst on-treatment value (for laboratory tests where NCI CTCAE grades are not defined, shift tables using the low/normal/high/[low and high] classification to compare baseline to the worst on-treatment may be generated).
- Listing of all laboratory data with values flagged to show the corresponding NCI CTCAE grades and the classifications relative to the laboratory normal ranges.

In addition to the above-mentioned tables and listings, graphical displays of key safety parameters, such as scatter plots of actual or change in laboratory tests over time or box plots may be specified in the SAP.

12.9.3. Other Safety Data

Descriptive statistics for the actual values and/or the changes from baseline of vital signs (including systolic and diastolic blood pressure, heart rate, respiratory rate, and temperature) over time will be summarized.

Descriptive statistics of ECOG PS over time will be summarized by frequency. Shift tables may be provided for ECOG PS from baseline to worst value of post-baseline assessments.

Categorical analysis of QTcF intervals may be performed. Maximum QTcF intervals and maximum changes from baseline may also be summarized similarly in a separate display. ECG abnormalities if collected will be presented in a data listing.

Additional safety analyses may be performed if deemed necessary.

12.10. Pharmacokinetic Analyses

A population pharmacokinetics approach will be performed to assess typical and individual subject PK parameters. Descriptive statistics will be used to summarize PK concentrations at different nominal time points across subjects.

12.11. Pharmacodynamic Analyses

Descriptive statistics will be used to summarize 2-HG concentrations at different nominal time points across subjects. The potential relationship between plasma exposure of AG-120 and plasma 2-HG levels will be explored with descriptive and graphical methods as appropriate.

12.12. Exploratory Analyses

12.12.1. Analysis of PFS2

For subjects who cross over from the placebo arm to the AG-120 arm, PFS2 will be calculated from first dose of AG-120 to second documented disease progression per Investigator (or death). The new baseline for response assessment for subjects who crossed over will be the progressive disease scan prior to cross over. For subjects who cross over who receive palliative radiotherapy after unblinding and during the cross over period, the new baseline for response assessment will be the MRI or CT scan obtained at the end of the 2-week washout period after radiotherapy. In the event that more than 1 scan is obtained, the latest scan prior to the first dose of AG-120 will be used as the new baseline. Kaplan-Meier estimates of PFS2 will be presented, including estimates of the median and other quantiles, as well as individual time points (eg, 3-month, 6-month, and 12-month rates).

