Pre-Screening Period (Optional): A banked tumor sample (the most recent one available, preferably collected within the last 3 years) or fresh tumor biopsy is required for confirmation of IDH1 gene mutation status by central laboratory testing, as part of the subject's eligibility for enrollment (R132C/L/G/H/S mutation variants tested). Potential subjects will sign a pre-screening consent for the purpose of determining IDH1 mutant status. (Potential subjects who do not provide a sample at pre-screening will provide one at Screening.)

Pre-Treatment/Screening Period: Following informed consent, all subjects will undergo Screening procedures to determine eligibility within 28 days prior to the start of study treatment on Cycle 1, Day 1 (C1D1), with the exception of baseline radiographic scans, which should be performed within 21 days prior to C1D1. If a tumor sample is not collected during the pre-screening period, a banked or fresh biopsy at Screening will be collected. Additional Screening procedures include review of entry criteria, recording of demographics and disease history, medical, surgical, and medication history, radiographic evaluation to determine extent of disease

(computed tomography [CT] or magnetic resonance imaging [MRI]), complete physical examination (including height/weight), vital signs, ECOG PS, 12-lead ECG, echocardiography (ECHO) (or other methods according to institutional practice) for LVEF (according to institutional standard of care), a buccal swab for germ-line mutation and DME related gene polymorphism analysis, plasma sample for circulating tumor DNA, clinical laboratory assessments (hematology, serum chemistry, coagulation, urinalysis, and serum pregnancy test), and blood samples for exploratory biomarker measurement.

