Primary Endpoint Results and Subsequent Study Unblinding: Once the primary endpoint of PFS (based on central radiology RECIST 1.1 assessment) is statistically analyzed, the Sponsor will communicate the topline aggregate results of the study via public disclosure, which will include participating study teams. Shortly after public disclosure of the topline aggregate results, the Sponsor will communicate to all sites that treatment assignments of all subjects will be unblinded and will also inform sites which of the 2 following scenarios to pursue following unblinding.

If the primary endpoint is statistically positive, all ongoing subjects (AG-120 and placebo-treatment assigned subjects) will be given the opportunity to receive open-label AG-120 following unblinding. Unblinding will no longer be contingent upon documented radiographic disease progression. Subjects who were already receiving AG-120 may continue to receive AG-120 on the same assessment schedule. Subjects who were receiving placebo and continue to meet cross-over eligibility criteria will be given the opportunity to receive open-label AG-120. For subjects who cross over, placebo will not be counted as a prior line of therapy for the purpose of eligibility. If subjects cross over, they will follow the same assessment schedule as

from CID1. Prior to crossing over, these subjects will undergo a CT or MRI that will serve as the new baseline against which all subsequent RECIST v1.1 assessments will be performed. If the subject has undergone a recent CT or MRI (≤ 3 weeks prior to start of cross-over treatment), the scan does not need to be repeated. Palliative radiotherapy to treat symptomatic pre-existing or new non-target lesions (per RECIST v1.1) that cannot otherwise be medically managed will be permitted after unblinding has occurred. AG-120 should be held for the duration of palliative radiotherapy. A 2-week washout from completion of radiotherapy will be required prior to starting or resuming AG-120. For subjects receiving palliative radiotherapy prior to the first dose of open-label AG-120, a repeat CT or MRI will be performed upon completion of the 2-week washout period to document the area that was irradiated and to serve as the new baseline. All decisions to pursue palliative radiotherapy will require Sponsor and/or Medical Monitor approval.

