If the primary endpoint is statistically positive, all ongoing subjects (AG-120 and placebo-treatment assigned subjects) will be given the opportunity to receive open-label AG-120 following unblinding. Unblinding will no longer be contingent upon documented radiographic disease progression. Subjects who were already receiving AG-120 may continue to receive AG-120 on the same assessment schedule. Subjects who were receiving placebo and continue to meet cross-over eligibility criteria will be given the opportunity to receive open-label AG-120. For subjects who cross over, placebo will not be counted as a prior line of therapy for the purpose of eligibility. If subjects cross over, they will follow the same assessment schedule as from C1D1. Prior to crossing over, these subjects will undergo a CT or MRI that will serve as the new baseline against which all subsequent RECIST v1.1 assessments will be performed. If the subject has undergone a recent CT or MRI (≤ 3 weeks prior to start of cross-over treatment), the scan does not need to be repeated. Palliative radiotherapy to treat symptomatic pre-existing or new non-target lesions (per RECIST v1.1) that cannot otherwise be medically managed will be permitted after unblinding has occurred. AG-120 should be held for the duration of palliative radiotherapy. A 2-week washout from completion of radiotherapy will be required prior to starting or resuming AG-120. For subjects receiving palliative radiotherapy prior to the first dose of open-label AG-120, a repeat CT or MRI will be performed upon completion of the 2-week washout period to document the area that was irradiated and to serve as the new baseline. All decisions to pursue palliative radiotherapy will require Sponsor and/or Medical Monitor approval.

If the primary endpoint is statistically negative, all ongoing AG-120 subjects will be permitted to continue receiving open-label AG-120 following unblinding at the discretion of the treating investigator. Palliative radiotherapy will be allowed for subjects who continue receiving AG-120 as described in the preceding “statistically positive” paragraph. Subjects who were receiving placebo will not be permitted to receive open-label AG-120 in this scenario and will come off study.

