8.8. Post Crossover

Upon the radiographic progression of disease, subjects will be unblinded. If it's determined that they received placebo, subjects will be allowed to cross over to AG-120, provided they continue to be eligible for the study. Data after crossover will be analyzed separately, but in a similar fashion as outlined above.

In particular, tumor assessments after crossover will be based on Investigator assessment. Tumor measurements will be re-baselined prior to the start of crossover. The corresponding endpoints include:

- PFS per Investigator assessment (PFS2)
- Objective response rate /best overall response per Investigator assessment. Note that SD<38 days of the first AG-120 dose date will be assigned as UNK.
- Time To Response and DOR per Investigator assessment

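### The progression-route crossover baseline scan has no age limit, so untreated growth before the first AG-120 dose counts toward progression in the exploratory PFS2

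*Protocol*

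**What the plan says.** The documents describe two routes from placebo to AG-120 and give each its own baseline-scan rule.

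- **Study-unblinding route** (Protocol synopsis, 7.1 and 9.6, after a positive primary result): "these subjects will undergo a CT or MRI that will serve as the new baseline against which all subsequent RECIST v1.1 assessments will be performed". An existing scan can serve only within a limit: for a "recent CT or MRI (≤ 3 weeks prior to start of cross-over treatment), the scan does not need to be repeated".
- **Progression route** (Protocol 12.12.1): "The new baseline for response assessment for subjects who crossed over will be the progressive disease scan prior to cross over". No maximum age is attached. The exception is palliative radiotherapy, after which "the new baseline for response assessment will be the MRI or CT scan obtained at the end of the 2-week washout period after radiotherapy".
- **More than one scan** (Protocol 12.12.1): where several scans exist, the most recent one before AG-120 starts becomes the reference. This selects among scans that exist and does not call for another.
- **SAP 8.8**: "Tumor measurements will be re-baselined prior to the start of crossover". SAP 10.3 takes the closest assessment before AG-120. Neither gives an age limit.
- **Initial treatment** (Protocol 7.1): screening falls within 28 days of C1D1, "with the exception of baseline radiographic scans, which should be performed within 21 days prior to C1D1".

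PFS2 is an exploratory endpoint, timed from the first AG-120 dose to the second progression per Investigator, or death (Protocol 12.12.1). SAP 8.8 also reports post-crossover ORR per Investigator.

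**The concern.** On the progression route the clock and the reference measurement can start on different days. Time runs from the first AG-120 dose. Tumour change runs from a scan taken earlier, when disease had just been called progressive on placebo. After that scan come consultation with the Medical Monitor, unblinding, and an eligibility check based on the EOT Visit. No passage limits the total time from the progression scan to crossover C1D1.

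Growth in that interval happens without AG-120 but uses up part of the margin to the next progression call. A new lesion that arises in the interval would be read as progression after crossover, however the drug performs. For response, a 30% fall must be reached from a baseline sum smaller than the tumour at first dose. Both effects run against AG-120. What is at stake is the description of what placebo subjects gained after crossing over, not the randomised comparison.

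**Working it through.** There is no planned figure to reproduce; the documents state no growth rate and no scan-to-dose interval. The check has two parts.

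**1. Is the age of the baseline scan bounded on each route?**

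- Study-unblinding route: yes, at most 3 weeks (21 days) before crossover treatment.
- Progression route: no. The 21-day window in Protocol 7.1 belongs to Screening. Crossover subjects resume at C1D1 and qualify from EOT Visit procedures (Table 3, footnote 1), so they have no new Screening period. Protocol 7.1 requires a scan at EOT only when treatment stopped for reasons other than progression or a new anticancer agent. The latest-scan rule and SAP 10.3 help only if a newer scan happens to exist.

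**2. How much could the gap matter?**

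Assume that the sum of diameters grows exponentially without treatment and takes T days to rise 20%. For a gap of g days from baseline scan to first dose:

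- growth before the first dose = 1.2^(g/T) − 1
- further growth needed to reach the 20% threshold (Protocol Appendix 15.9, Table 6) = 1.2 / 1.2^(g/T) − 1
- fall from the first-dose size needed for a 30% reduction from baseline = 1 − 0.70 / 1.2^(g/T)

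T is an assumption and is varied. T = 42 days is one 6-week scan interval. T = 68 days is the longest interval from initial baseline to first scheduled scan that the windows allow (21 + 42 + 5). T = 182 days is 26 weeks. The gaps are also illustrative: 21 days is the protocol's own scan window, and 33 days is the longest EOT window.

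| T | Gap | Growth before first dose | Further growth to 20% | Fall needed for 30% response |
|---|---|---|---|---|
| 42 d | 21 d | 9.5% | 9.5% | 36.1% |
| 42 d | 33 d | 15.4% | 4.0% | 39.3% |
| 68 d | 21 d | 5.8% | 13.4% | 33.8% |
| 68 d | 33 d | 9.3% | 9.8% | 35.9% |
| 182 d | 21 d | 2.1% | 17.5% | 31.5% |
| 182 d | 33 d | 3.4% | 16.1% | 32.3% |

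Example: 1.2^(33/42) = 1.154, so growth is 15.4%; 1.2/1.154 − 1 = 4.0%; 1 − 0.70/1.154 = 39.3%.

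Two limits apply. The progression rule also needs an absolute increase of at least 5 mm. And once the sum falls below the crossover baseline on AG-120, the smallest sum becomes the reference, so later target-lesion progression calls no longer carry the pre-dose growth.

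**The case against.** The strongest reply is that the gap may be short and the consequence small.

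- **The 33 days are not a scan-to-dose interval.** They run from last dose to the EOT Visit and allow for held dosing; without a delay the EOT Visit falls within 5 days of last dose (Protocol 10.1). Scans continue during dose holds, so a held subject's progression scan may come well after the last dose. This stands: 33 days is an example, neither a documented gap nor an upper bound.
- **20% in 42 days is not a minimum growth rate.** Progression is judged against the smallest sum, so 20% can accumulate over several scans, and new or non-target lesions count with no target growth at all. This stands, and is why slower rates are shown.
- **A 3-week limit also admits pre-dose growth**, up to 9.5% at the fastest rate above. This stands. The difference between routes is one of degree and of having a bound.
- **A newer scan may be implied.** Table 3 marks a tumour assessment at EOT under a footnote that does not exempt progression. Protocol 7.1 reads differently and 12.12.1 names the progression scan, so this is a further reason to reconcile the text.
- **Two rules are not in themselves a contradiction.** Unblinding-route subjects may have no progression scan and need their own rule. This stands, but 12.12.1 words its rule for crossover subjects generally and so does not fit them.

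A reader might infer more than this supports. Pre-dose growth counts toward progression; under this model it reaches 20% alone only when the gap is as long as T. Nor do the documents show that PFS2 cannot be pooled across routes. The SAP follows Amendment 4, before the unblinding language was added, and its Crossover Set (6.4) covers only crossover on radiographic progression, although Protocol 12.3 defines the set more widely. No comparison of PFS2 with the randomised AG-120 arm is planned.

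**Conclusion.** The concern holds in a limited form. The baseline scan's age is bounded on the study-unblinding route and unbounded on the progression route, while PFS2 starts at the first AG-120 dose on both. Where the progression scan is old, PFS2 and post-crossover ORR are biased against AG-120.

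The documents do not determine the size. For a 33-day gap the illustration gives 3.4% to 15.4% growth before dosing, set against a 20% threshold. It rests on assumed exponential growth, assumed rates and an assumed gap.

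The reach is narrow: PFS2 is exploratory, single-group, Investigator-assessed and untested. A reader might infer that the trial's main conclusions are touched. They are not: primary PFS and OS do not use this baseline, and the testing sequence of IRC PFS, OS and IRC ORR is unaffected.

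**What to change.** In SAP 8.8, derive for each crossover subject the days from baseline scan to first AG-120 dose, and summarise that interval. Report PFS2 and post-crossover ORR overall and, as a sensitivity analysis, restricted to subjects whose baseline scan was within 21 days of the first AG-120 dose. That cut-off is the protocol's existing window.

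This uses dates already collected and needs no added procedure. The cost is one derived variable and one extra run. The restricted subset will be less precise, and its members may differ in other ways from those who crossed over later, so a difference between the two results should not be put down to scan age alone.

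Separately, Protocol 7.1, 9.6 and 12.12.1 and SAP 8.8 must be reconciled on which scan is the crossover baseline, including for unblinding-route subjects who have no progression scan. The text should state one scan-age rule or give a reason for two. Which rule applies is for the sponsor to decide.
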